7.2.2 Sampling technique

All patients who are identified using the retrospective searches, and who meet the eligibility criteria, will be included. Sampling techniques to reduce this cohort size will not be used because rupture events are uncommon and sampling may lead to an underrepresentation of the true rupture rate if these patients are missed. Furthermore, the final cohort size needs to be as large a possible in order to accurately include uncommon prognostic factors such as APCKD in the final model.

7.3 Recruitment

7.3.1 Sample identification

Patient identification

Due to most UIAs being detected during investigation for other conditions, HES coding for outpatient appointments cannot reliably identify patients with intracranial aneurysms and a local review suggested this may lead to a large underestimate of cases.

Therefore, patients will be identified by the direct clinical care teams at adult tertiary neurosurgical units in the UK treating patients with UIAs. All patients will be eligible whether seen in the centre, scanned in the centre or only discussed with the centre at MDT or on-call. Therefore, more than one search method may be applicable. Search methodology may be adapted to suit local case note and radiology records. We would recommend sequentially performing the following searches:

- 1. Electronic keyword searches of clinic letters, discharge summaries and MDTs. These capture most patients but risk missing patients not formally discussed with neurosurgery.
- 2. Electronic searches of cranial CTA, MRA and DSA reports for the term "aneurysm" excluding "no aneurysm". These searches capture all patients at the parent hospital but may miss regional patients scanned in district hospitals.
- 3. Searches of on call referrals may capture any further conservatively managed UIAs.

In some units, paper records of MDT or vascular clinics may be searched where electronic systems are not in place. Additionally, some units maintain prospective neurovascular databases which could be used for patient identification.

To reduce selection bias all participating centres will produce a written search strategy for their unit and perform a search over a locally prespecified time period. This period will be within the range of 1 January 2006 – 31 December 2020 (representing the implementation of PACS and the present), but may be shorter. The date of inclusion will be the date of the first document to identify the patient in that locally prespecified date range. Where aneurysms were diagnosed before the study dates, the aneurysm will be marked as "known diagnosis" and the date of inclusion remains that of the first document in the study date range.

Patients will not be contacted as part of the identification process. There will also not be any payments made to the patients. There will not be any recruitment through publicity adverts. The study will have a dedicated website which will contain details of the study designed for investigators but this will not be used as a source of recruitment.

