4 RESEARCH QUESTION/AIM(S)

Primary Aims:

Aim 1 - To validate the PHASES score in a UK population.

- Aim 2 To develop a new prediction model including all described predictors of risk.
- Aim 3 To report long-term risk of aneurysm rupture.

Secondary Aims:

Aim 4 – To develop risk models of aneurysm growth.

Aim 5 – To evaluate the efficacy of aneurysm screening regimens.

Aim 6 – To develop and evaluate new radiological predictors of aneurysm growth and rupture.

5 STUDY DESIGN and METHODS of DATA COLLECTION AND DATA ANALYIS

Data Collection – Baseline data – local neurosciences units Patients will be identified by members of the clinical care team and record:

- NHS number
- Name
- Date of birth
- Post code

These patients will be allocated a study number for pseudonymisation. This data will not be otherwise kept or used for other research purposes.

Further data will be collected from patient's case notes (either electronic or paper based as appropriate). A separate data definitions manual will be produced. All data collectors will be provided with a mandatory education module and correctly collect data from test cases before data collection.

The core covariates for each patient at time of diagnosis will be:

- Date of first diagnosis of aneurysm (date of first CTA/MRA/DSA or where not available date of first MDT or clinic appointment whichever is earlier)
- Date of inclusion in the study (date of first CTA/MRA/DSA or where not available date of first MDT or clinic appointment that lies within the unit's search period)
- Hypertension: a co-morbidity of hypertension or regular use of anti-hypertensive medication at time of diagnosis.
- Age: in years at time of diagnosis of aneurysm on angiographic imaging
- Gender:
- Site: anterior cerebral artery (including anterior communicating and pericallosal arteries), internal carotid (including bifurcation, ophthalmic, superior hypophyseal), MCA (including M1 segment and bifurcation), posterior communicating and posterior circulation (including vertebral, basilar, cerebellar and posterior cerebral arteries).
- Aneurysm size: the longest aneurysm dimension recorded to the nearest millimetre as described by the MDT discussion or where not available from the reporting radiologist at time of diagnosis or where not available from the clinic letter.
- Previous aneurysmal subarachnoid haemorrhage: confirmed diagnosis of aneurysmal SAH in the patient's medical history.

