- Population: European/North American, Finnish, Japanese (where race cannot be confirmed it will be assumed to be non-Finnish and non-Japanese on the basis that there is a low incidence of these populations in the UK and their presence would usually be considered noteworthy in a clinical note.

The additional desirable covariates at time of diagnosis will include:

- aspirin use any dose used >3* per week
- statin use any statin use >3* per week
- smoking history non-smoker, ex-smoker, current smoker
- Aneurysm multiplicity record number of intra-dural aneurysms the patient has (treated or untreated)
- Family history number of 1 first degree and second degree relatives with UIA/SAH
- History of Autosomal Dominant Polycystic Kidney Disease yes, no
- Aneurysm location subclassification ICA paraclinoid (ophthalmic and superior hypophyseal) ICA (PCom), ICA other (anterior choroidal and bifurcation), ACA ACOM, ACA pericallosal, MCA, Posterior (basilar termination), Posterior (SCA), Posterior (AICA) Posterior (PICA)
- Bleb or irregularity of aneurysm recorded as present or absent from radiology report only. If not mentioned in report assumed to be absent. If no radiology report available, then recorded as NA.
- New/known diagnosis: patients in whom the aneurysm was known prior to the search period will be recorded as known diagnosis and otherwise as new diagnosis.

Data collection – aneurysm rupture/censoring events – local neurosciences units

At the time of baseline data collection locally available follow up will be recorded which will include:

• Date of last follow-up

- Date of death (if applicable)
- Cause of death (if applicable)
- Date of SAH (if applicable)
- Location of aneurysm causing SAH (if applicable)
- Date of aneurysm treatment (if applicable)
- Reason for aneurysm treatment (if applicable)

This data will be used for quality control of subsequent HES searches.

Data collection - aneurysm rupture/censoring events - central HES ONS data

Upon collection of all baseline data, a search of the Hospital Episode Statistics (HES) and Office for National Statistics (ONS) databases using the patient's NHS numbers be conducted. The use of a HES and ONS search is designed to maximise the identification of rupture events which are not treated in neurosurgical unit as subarachnoid haemorrhage. It will thus identify events managed in a district general hospital or those who die pre-hospital.

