Complete anonymisation of data is not possible due to HES and ONS searches and similar searches in Wales and Scotland. The minimum level of identifiable data for HES searches are NHS number and date of birth. Inclusion of name and post-code is highly advantageous for more reliable 3 point searches in view of likely typographical errors with large numbers of NHS numbers. Therefore, permission to use this limited identifiable data will be sought.

It is anticipated that as this represents research performed by a public body that is in the public interest and cannot viably be performed in another way, that explicit patient consent will not be required for GDPR. The reason it cannot be performed with explicit patient consent is that many patients who suffer SAH are left dead or without capacity. These patients would therefore not be able to consent and participate leading to an underestimate of aneurysm rupture rates. Under the NHS Act

2006, a section 251 waiver for consent to confidential data will be requested from CAG. In order to meet the requirements of proportionality and minimization of data use, the following methods will be used.

Patients will be identified by the local clinical care team. In view that the inclusion criteria for the study require review of the majority of variables that will be collected in the study, on identification patient details and clinical details will be collected at the same time and a study number allocated for pseudonymisation. These will be held securely on password protected local hospital computers.

Each recruiting unit will upload their patient NHS numbers to the NHS Spine to check for a patient's pre-registered wish to opt out of their data being used for research. The NHS Spine will return a list of NHS numbers for patients who have not registered to opt out of research. Each recruiting unit will destroy the details for any other their patients who are not on the list returned from NHS Spine.

All data will be transferred between investigators using secure NHS email communication (NHS.net). All data will be stored on NHS Trust servers or encrypted mobile data devices. No data will be saved to unsecured personal computers.

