7 SAMPLE AND RECRUITMENT

7.1 Eligibility Criteria

7.1.1 Inclusion criteria

- 1. Age 18 years or older.
- 2. Intracranial intradural unruptured aneurysm.
- 3. Confirmed on angiogram (CTA/MRA/DSA).

4. Diagnosis of UIA between January 2006-December 2020.

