7.1.2 Exclusion criteria

- 1. Mycotic or vasculitic aneurysms.
- 2. Aneurysm diagnosed on CT or MRI alone.
- 3. AVM associated flow aneurysms.
- 4. Extradural aneurysms (e.g. intra-cavernous).
- 5. Aneurysms previously treated by either microsurgical or endovascular techniques.
- 6. Small lesions uncertain as to whether they are truly aneurysmal ("dilatation", "bulge", 'Infundibulum", etc)

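### The protocol gives two different dates of inclusion and no date at which eligibility is judged, so entry can precede angiographic confirmation and inclusion can depend on later events

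*Protocol*

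**What the plan says.** **Two definitions of entry.** Protocol section 5 (baseline data, core covariates) defines the date of inclusion as "date of first CTA/MRA/DSA or where not available date of first MDT or clinic appointment that lies within the unit's search period". Section 7.3.1 says: "The date of inclusion will be the date of the first document to identify the patient in that locally prespecified date range". The sources searched under 7.3.1 include clinic letters, discharge summaries, MDT records, radiology reports and on-call referrals. The identifying document therefore need not be an angiogram report.

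**Undated criteria.** Section 7.1.1 requires "Intracranial intradural unruptured aneurysm" (inclusion 2) and "Confirmed on angiogram (CTA/MRA/DSA" (inclusion 3). Section 7.1.2 removes "Aneurysm diagnosed on CT or MRI alone" (exclusion 2) and "Small lesions uncertain as to whether they are truly aneurysmal" (exclusion 6). None of the four says as of which date it must hold.

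**Outcome in view.** Section 5 (local rupture and censoring events) states: "At the time of baseline data collection locally available follow up will be recorded which will include", and the list includes the date of SAH. Section 5 (patient confidentiality) adds that "on identification patient details and clinical details will be collected at the same time". No blinding of the eligibility decision to outcome is described.

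**The concern.** In a cohort study, eligibility should be decided on what was known at time zero. Here the two entry rules can give one patient two different time zeros, and one of them allows entry before the evidence that makes the patient eligible.

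Two opposite biases follow. A haemorrhage usually leads to angiography, whereas a quiet, doubtful lesion may never have it. If imaging at rupture may satisfy inclusion 3 or settle the doubt under exclusion 6, bleeding lesions are admitted and comparable quiet ones are not. Conversely, a lesion confirmed electively some time after its first document carries the interval in between as guaranteed event-free time, unless imaging at rupture is accepted.

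Aim 1 reports an absolute 5-year risk for each PHASES score, and a few events wrongly admitted or lost matter most in sparse strata. Section 5 (Aim 1) plans corrections mainly for underestimation and expects no material overestimation, because SAH events are verified in the notes. Verification removes false events. It does not remove true events in patients who became eligible only because they bled. The final comparison with local follow-up would not detect the problem either, since it uses the same selected cohort.

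**Working it through.** **1. The two entry rules applied to the same cases** (illustrative dates)

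| Case | Section 5 | Section 7.3.1 |
|---|---|---|
| Plain MRI and MDT 2010; first DSA at rupture 2014, in range | Entry 2014, no longer unruptured, so not eligible | Entry 2010 with an event, if the 2014 DSA may satisfy inclusion 3 |
| Same, but the unit's search period ends before 2014 | Fallback to the 2010 MDT date is arguable; event counted if the later DSA is accepted | Entry 2010 with an event, on the same condition |
| Plain MRI and MDT 2010; never bleeds, no angiogram | Excluded (inclusion 3, exclusion 2) | Excluded |
| Letter 2010; elective angiogram 2012, in range | Entry 2012 | Entry 2010, two years event-free by construction |

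The rules disagree in the first and fourth rows. In the second row the section 5 fallback does not close the gap.

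**2. The protocol's planning rate.** Section 7.2.1 takes 51 ruptures in 1,692 patients over 4.1 years. The rate is 51/(1,692 × 4.1) = 0.735% per year. Sixty events need 60 × 1,692/51 = 1,990.6 patients and 1,990.6 × 4.1 = 8,161 years, which reproduces the stated 1,990 and 8,161. This point disputes neither figure. The corresponding 5-year risk is p = 1 − (1 − 51/1,692)^(5/4.1) = 3.66%.

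**3. Sensitivity of the 5-year risk.** Four quantities are needed:
- p: true 5-year risk, taken as equal in confirmed and unconfirmed lesions;
- u: lesions unconfirmed or doubtful at the first document, per confirmed lesion;
- q: share of the unconfirmed lesions that bleed which end up confirmed and included;
- e: the same share among those that do not bleed.

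Observed/true = (1 + u·q) / (1 + u·[p·q + (1 − p)·e]).

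Only p can be taken from the protocol. The values of u, q and e are assumptions. At p = 3.66%:

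| q | e | u = 5% | u = 10% | u = 25% | u = 50% |
|---|---|---|---|---|---|
| 1 | 0 | 1.05 | 1.10 | 1.24 | 1.47 |
| 1 | 0.5 | 1.02 | 1.05 | 1.11 | 1.19 |
| 0.5 | 0.5 | 1.00 | 1.00 | 1.00 | 1.00 |
| 0.25 | 0.5 | 0.99 | 0.98 | 0.95 | 0.90 |
| 0 | 0.5 | 0.98 | 0.95 | 0.89 | 0.81 |

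Example: u = 25%, q = 1, e = 0 gives 1.25/(1 + 0.25 × 0.0366) = 1.24. At an assumed p = 0.5% the first row becomes 1.05, 1.10, 1.25 and 1.50, so the ratio depends little on p.

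**4. Reading the table.** The sign depends on whether q exceeds e. The last two rows also show that barring rupture imaging while leaving entry at the first document is not enough. Ruptures before confirmation would be dropped and the event-free time before confirmation kept, which biases risk downward.

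**The case against.** The strongest reply is that section 5 already gives the right rule. With entry at the first in-range angiogram, a lesion first imaged at rupture enters when it is no longer unruptured, and one confirmed in 2012 enters in 2012. The 7.3.1 sentence also has a proper use: where a known aneurysm was imaged before the search range, the first in-range document correctly starts time at risk. Abstraction rules may sit in the separate data definitions manual, which is not shown, and collectors are trained on test cases. Many ruptures occur at other hospitals and surface only through the HES/ONS linkage after the cohort is assembled, so sites often could not select on them.

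Much of this stands. Section 5, if applied together with inclusion 2, largely closes the upward route. It does not remove the conflict, because 7.3.1 states its rule generally and not only for known diagnoses. Nor does it cover the fallback. Late linkage limits selection but does not exclude it, since sites record locally known SAH and search discharge summaries. Entry date and eligibility belong in the protocol, and a manual cannot settle two protocol sections that disagree.

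A reader might infer something stronger: that the plan admits doubtful lesions if they bleed, excludes them if they do not, and so inflates risk in small aneurysms. The documents do not support that. No section says imaging at rupture may settle eligibility; it is only not forbidden. Quiet lesions can be confirmed later by elective angiography. Exclusion 6 names small lesions but exclusion 2 has no size limit, so concentration in small aneurysms is plausible and not shown.

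**Conclusion.** The point holds as a conflict between sections 5 and 7.3.1 over time zero, together with eligibility criteria that have no as-of date. Where 7.3.1 or the section 5 fallback is followed, entry can precede confirmation and inclusion can depend on outcome.

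Neither the net direction nor the size can be computed. The documents give no count of lesions unconfirmed at first document and no later-confirmation rates. The ratios of 0.81 to 1.50 rest on assumed u, q and e, on equal rupture risk in confirmed and unconfirmed lesions, and on q and e values chosen to span the possibilities. They show that the effect could matter at either end and do not estimate it. The protocol's sample-size figures are unaffected. The change should be made before sites collect data, because time zero is hard to reconstruct afterwards.

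**What to change.** 1. Use one definition in sections 5 and 7.3.1: time at risk starts at the later of (a) the first unit document in the search range and (b) the first CTA, MRA or DSA confirming the intradural aneurysm. For known diagnoses, (b) may predate the range.
2. State in section 7.1 that every inclusion and exclusion criterion is judged on documents dated on or before that date.
3. State that imaging done at or after rupture of the index aneurysm cannot satisfy inclusion 3 or resolve exclusion 6. Limit this to the index aneurysm. Unruptured aneurysms found on imaging for an earlier SAH from a different aneurysm must stay eligible, because previous SAH is a PHASES item and a wider bar would strip that predictor from the validation.
4. Where feasible, complete the eligibility form before later records are opened.
5. Report how many lesions were confirmed only after their first document.

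Items 1 and 3 are both needed: item 3 alone would leave the downward bias in place.

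The cost is protocol and data-manual wording. Some patients will enter later, and some will be lost where the confirming angiogram cannot be dated.

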7.3.2 Consent

Informed consent will not be sought from the patients included in this study. The practicalities of approaching over 10,000 patients for consent would be logistically challenging and in attempting to obtain consent from such a large group of patients it would be expected there will be a significant number of patients in whom no consent can be obtained for practical reasons. We would expect it much less likely to be possible to obtain consent in patients who had suffered a bleed from an unruptured aneurysm as they are likely to be left either incapacitated, or dead. Therefore, if the study only included patients with informed consent, it would include far fewer cases who suffered a rupture leading to underestimates of the risk of bleeding and give misleading results – i.e. the requirement for full informed consent would heavily bias the study and invalidate the results.

Whilst informed consent won't be sought we will be respecting a patient's right to opt out of having their data used for research. All patients identified by the recruiting unit will be screened against the NHS Spine for patients who have registered as part of the National Data Opt-Out.

8 ETHICAL AND REGULATORY CONSIDERATIONS

The sponsor will ensure that the trial protocol and submitted supporting documents have been approved by the appropriate regulatory body, Health Research Authority (HRA), main research ethics committee (REC) and that local permission has been obtained prior to any subject identification.

Health Research Authority

All substantial amendments and non-substantial amendments (as determined by the sponsor) will not be implemented until HRA/REC have provided the relevant authorisations. The NHS R&D departments will also be informed of any substantial amendments and non-substantial amendments. Relevant approvals must be obtained before any substantial amendment and non-substantial amendments may be implemented at sites.

All correspondence with the HRA and the REC will be retained in the Trial Master File and the Investigator Site File (maintained by the site).

An annual progress report (APR) will be submitted to the REC within 30 days of the anniversary date on which the favourable opinion was given, and annually until the trial is declared ended.

Within 90 days after the end of the trial (as defined in section 7.10), the CI/Sponsor will ensure that the HRA and the main REC are notified that the trial has finished. If the trial is terminated prematurely, those reports will be made within 15 days after the end of the trial.

The CI will supply the Sponsor with a summary report of the clinical trial, which will then be submitted to the main REC within 1 year after the end of the trial.

All results will be published on a publicly accessible database.

8.1 Assessment and management of risk

This research proposal is based on retrospective data collection from already established medical records. There will be no direct patient contact. The retrospective design means that the conduct of this study cannot alter the treatment they have already received. Thus, there are no direct risks nor burdens to their health.

The risk to patients from this study is associated with breach of confidentiality and any harm this could cause. Most access to patient identifiable data will be by the direct clinical care team who would have routine access to the patient's medical records and poses minimal risk. There is a small risk of data being exposed during transfer to the coordinating centre. We have attempted to minimise risk/burden to the patient from confidentiality breach by separating clinical details and patient identifiable details into different datasheets. These datasheets will be transferred independently with the patient identifiable details transferred using a separate AES-256 bit end-to-end encryption software such as Slack. Therefore, in the unlikely event of a breech, clinical data could not be linked to patients. Outside of the direct clinical care team only the co-ordinating centre will have access to both the clinical and identifiable details which will be minimised as much as possible by deleting the identifiable details as soon as they have been uploaded to HES/PEDW/SMR.

